3.2	SECONDARY OBJECTIVES.....	10
4.0	STUDY DESIGN	10
4.1	INCLUSION CRITERIA.....	10
4.2	EXCLUSION CRITERIA	10
5.0	STUDY PROCEDURES	11
5.1	SCREENING AND ENROLLMENT	11
5.2	RANDOMIZATION	11
5.3	INTERVENTIONS.....	11
5.4	BLINDING.....	13
5.5	ASSESSMENTS	13
6.0	MONITORING	14
7.0	STATISTICAL ANALYSIS PLAN	15
7.1	DEFINITIONS.....	15
7.2	OUTCOME MEASURES	16
7.3	SAMPLE SIZE.....	17
7.4	ANALYSIS	18
8.0	ETHICS AND REGULATORY	19
8.1	ETHICAL STANDARDS.....	19
8.2	DATA CONFIDENTIALITY.....	19
8.3	DATA HANDLING AND RECORD KEEPING	19
9.0	PUBLICATION POLICY	20
10.0	REFERENCES	22
	APPENDIX I – SCHEDULE OF ASSESSMENTS	24

List of Abbreviations

ANC	Absolute neutrophil count
ARLG	Antibacterial Resistance Leadership Group
AS	Antimicrobial stewardship
AST	Antimicrobial susceptibility testing
AXDX	Accelerate Pheno™System
CDC	Centers for Disease Control and Prevention
CRF	Case report form
DCRI	Duke Clinical Research Institute
DOOR/RADAR	Desirability of outcome response and response adjusted for days of antibiotic risk
EMR	Electronic medical record
FDA	Food and Drug Administration
FISH	Fluorescent in situ hybridization
FSTRF	Frontier Science Technology and Research Foundation
GNB	gram-negative bacilli
ICMJE	International Committee of Medical Journal Editors
ICU	Intensive care unit
ID	Infectious diseases
IRB	Institutional review board
IV	By vein
MALDI-TOF MS	Matrix-assisted laser desorption/ionization mass spectrometry
MDRO	Multi-drug resistant organism
NIAID	National Institutes of Allergy and Infectious Disease
NIH	National Institutes of Health
NHSN	National Healthcare Safety Network
PCR	Polymerase chain reaction
PO	By mouth
SD	Standard deviation
SDMC	Statistics and data management center
SOC	Standard of care
VAP	Ventilator-associated pneumonia

Protocol Synopsis

Protocol Title:	Rapid Identification and Phenotypic Susceptibility Testing for Gram-Negative Bacteremia (RAPIDS-GN)
Study Design:	Multi-center, prospective, randomized, controlled trial to evaluate the following strategies for patients with confirmed gram-negative bacillus bacteremia: 
 1) Standard culture and antimicrobial susceptibility testing (AST); or 2) Rapid identification and AST using the Accelerate PhenoTest™ BC Kit, performed on the Accelerate Pheno™ System (AXDX)
Primary Study Objectives:	To evaluate the impact of rapid identification and AST on time to first antibiotic modification in the first 72 hours after randomization
Secondary Objectives	To evaluate the impact of rapid identification and AST on antimicrobial utilization and clinical outcomes. 
 • 30-day mortality • Length of stay in the hospital • Days in the ICU • Duration of broad-spectrum gram-negative coverage in the first 72 hours following randomization • Mean time to antibiotic escalation • Mean time to antibiotic de-escalation • Hospital-onset Clostridium difficile • Acquisition of new hospital-acquired infections (HAIs) and/or multidrug resistant organisms (MDROs)
Study Population	All patients with blood culture bottles growing gram-negative bacilli (GNB) detected on Gram staining will be eligible
Number of subjects	500 subjects
Number of sites	2 sites
Clinical Samples	Clinically collected blood cultures with growth of GNB detected by Gram stain
Start of Enrollment:	October 2017
End of Enrollment:	October 2018

1.0 Background Information and Scientific Rationale

1.1 Background Information

Novel molecular diagnostics to identify bacteria and determine antimicrobial susceptibility from clinical cultures are quickly entering the arsenal of tools used by clinical microbiology laboratories. However, the clinical benefit of these methods has not been well-quantified.

The goal of this study is to determine the impact of rapid bacterial identification and phenotypic antimicrobial susceptibility testing (AST) on antimicrobial usage and clinical outcomes.

The Accelerate PhenoTest™ BC Kit, performed on the Accelerate Pheno™ System (together termed AXDX) (Accelerate Diagnostics, Tucson, AZ) is an FDA-approved fully automated platform that performs rapid bacterial identification within 1.5 hours followed by determination of minimum inhibitory concentration (MIC)-based phenotypic susceptibility within approximately 7 hours directly from positive blood cultures.¹ This novel system uses fluorescence *in situ* hybridization (FISH) for rapid bacterial identification for a panel of organisms followed by time-lapse microscopy for determining phenotypic AST directly from positive blood culture bottles (see Table 1). In a study of 1850 blood cultures with gram-positive, gram-negative, or yeast isolates, AXDX was found to have overall 97.4% sensitivity and 99.3% specificity for organism identification compared to conventional culture methods (see Table 2). Among 728 gram-negative isolates, AXDX had 97.6% sensitivity and 99.6% specificity for pathogen identification, and had excellent essential (device result agrees exactly with or within one two-fold dilution of the reference result) and categorical (the device and reference result interpretive categories agree) agreement with the gold-standard methods for drug susceptibility testing, according to Food and Drug Administration (FDA) and/or Clinical and Laboratory Standards Institute (CLSI) breakpoints (see Table 3)¹.

Table 1. FDA-approved gram-negative bacilli and antibiotic combinations available on AXDX

	Ampicillin-sulbactam	Piperacillin-tazobactam	Cefepime	Ceftazidime	Ceftriaxone	Ertapenem	Meropenem	Amikacin	Gentamicin	Tobramycin	Ciprofloxacin	Aztreonam
E coli	x	x	x	x	x	x	x	x	x	x	x	x
Klebsiella spp.*	x	x	x	x	x	x	x	x	x	x	x	x
Enterobacter spp.*		x	x	x	x	x	x	x	x	x	x	x
Proteus spp.*	x	x	x	x	x	x	x	x	x	x	x	x
Citrobacter spp.*		x	x	x	x	x	x	x	x	x	x	x
S. marescens		x	x	x	x	x	x	x	x	x	x	x
P. aeruginosa		x	x	x			x	x	x	x	x	
A. baumannii		x						x				

**Klebsiella spp.* includes *pneumoniae* and *oxytoca*; *Enterobacter spp.* includes *cloacae* and *aerogenes*; *Proteus spp.* includes *mirabilis* and *vulgaris*; *Citrobacter spp.* includes *freundii* and *koseri*

Table 2. Clinical trial results of AXDX performance for gram-negative bacilli identification (N = 728)

Organism	Sensitivity (%)	Specificity (%)
A. baumannii	98.6	99.7
Citrobacter spp.	96.8	99.3
E. coli	97.3	99.7
Enterobacter spp.	97.3	99.5
Klebsiella spp.	96.1	99.6
P. aeruginosa	100	99.4
Proteus spp.	97.7	99.6
Serratia marcescens	100	99.9
Gram-negative bacilli, total	97.6	99.6

Table 3. Clinical trial results of AXDX performance for gram-negative bacilli antibiotic susceptibility.

Antibiotic	EA (%)	CA (%)	# of fresh isolates	# of challenge isolates
Amikacin	93.8	93.8	202	200
Ampicillin-sulbactam	91.0	82.7	174	92
Aztreonam	96.4	97.6	198	137
Cefepime	96.2	95.5	215	209
Ceftazidime	92.4	92.1	203	163
Ceftriaxone	94.7	96.4	180	124
Ciprofloxacin	98.4	98.4	216	209
Ertapenem	98.8	98.5	200	139
Gentamicin	99.5	98.7	207	165
Meropenem	96.7	96.9	215	208
Piperacillin-tazobactam	91.0	90.8	207	205
Tobramycin	96.3	96.0	210	165

EA, essential agreement; CA, categorical agreement; challenge isolates with key resistance phenotypes and genotypes were seeded into blood culture broths.

1.2 Scientific Rationale

Bacteremia due to gram-negative bacilli (GNB) poses a dangerous threat due to increasing rates of resistance and high mortality with ineffective antibiotic therapy.²⁻⁶ Conversely, treatment with overly broad antibiotics increases risks of adverse drug events and drives further development of resistance.^{7,8} An important solution to address this conundrum is development of methods for rapid detection of drug resistant GNB, which would allow for rapid de-escalation or escalation of antibiotics to appropriate definitive therapy.⁹ Standard turn-around-time for clinical microbiology laboratories to isolate, identify, and perform antimicrobial susceptibility testing (AST) of bacterial isolates is 48-96 hours from the time a blood culture turns positive, while rapid testing methods can provide results within 6-24 hours. Strategies for rapid phenotypic AST of GNB are preferred over methods for genotypic resistance detection, which cannot reliably predict the numerous antibiotic resistance mechanisms in GNB.^{2,10,11}

Prior single-center, observational studies have demonstrated decreased time to appropriate antibiotics, lower mortality, shorter durations of hospital and ICU stay, and reduced costs when rapid identification and AST methods are coupled with antimicrobial stewardship.¹²⁻¹⁴ Limitations to these studies include the fact that they were retrospective, subject to temporal trends, single-center, and uncontrolled. A previous single-center, randomized, controlled trial demonstrated that rapid polymerase chain reaction (PCR)-based identification paired with antimicrobial stewardship intervention was associated with more rapid antibiotic de-escalation, shorter time to appropriate antibiotic therapy, and less use of broad-spectrum antibiotics.¹⁵ However, the diagnostic test evaluated in that study had limited impact on management of patients with GNB bacteremia

because the test detected only a single GNB resistance determinant (*bla_{KPC}*), and did not provide rapid phenotypic susceptibility information for a full panel of antibiotics.

Accelerate's AXDX is the first FDA-approved platform to provide both identification and *rapid phenotypic antibiotic susceptibility* testing of organisms directly from positive blood cultures. We will evaluate the clinical impact of AXDX testing for GNB bacteremia in a multicenter, prospective, randomized, controlled clinical trial. This study will evaluate the impact of AXDX testing in the setting of baseline antimicrobial stewardship activities, because current regulations mandate that all acute care settings have antimicrobial stewardship programs,^{16,17} and several prior studies demonstrate benefit of combining rapid testing with antimicrobial stewardship. Results from this study will inform strategies to improve diagnostic testing for GNB bacteremia.

2.0 Hypotheses

We hypothesize that subjects with GNB bacteremia who receive rapid testing of blood cultures using AXDX will have faster time to antibiotic modification within the first 72 hours following randomization compared to subjects who receive standard bacterial culture and AST.

3.0 Objectives

3.1 Primary Objectives

The primary objective is to evaluate the impact of rapid identification and AST on time to first antibiotic modification in the first 72 hours after randomization.

3.2 Secondary Objectives

Secondary objectives will be to evaluate the impact of rapid identification and AST on antibiotic utilization and clinical outcomes.

4.0 Study Design

This study will be a multicenter, prospective, randomized, controlled trial evaluating antimicrobial utilization and clinical outcomes among patients with GNB bacteremia. Patients will be randomized to one of the following arms:

1. Standard culture and AST
2. Rapid identification and AST using AXDX

Baseline antimicrobial stewardship will occur in both arms. The blood sample for arm 2 will also undergo standard culture and AST in addition to the rapid testing.

4.1 Inclusion Criteria

Patients who meet the following inclusion criteria, and none of the exclusion criteria, will be included in the study:

- Positive blood culture with Gram stain showing GNB identified during local laboratory business hours.

4.2 Exclusion Criteria

Patients who meet any of the following criteria will be excluded from the study:

- Identification of GNB outside of local laboratory business hours (e.g. whenever laboratories are staffed to perform both rapid testing and routine testing)
- Positive blood culture for GNB at the same institution within prior 7 days (if known at the time of randomization).
- Deceased at the time of randomization.
 - GNB plus gram-positive organism, gram-negative cocci, and/or yeast detected on Gram stain
 - Previous enrollment in this study
- No Minnesota research authorization (*Rochester site only*)

If the patient does not meet any of the above exclusion criteria, he/she will be randomized, and laboratory testing will be performed according to group assignment.

5.0 Study Procedures

5.1 Screening and Enrollment

Eligible patients will be identified based on positive blood culture bottles with Gram stain showing GNB. The Microbiology Laboratory Technologists will screen for exclusion criteria and then will enroll patients who do not meet any exclusion criteria.

This study will not require informed consent because this FDA approved test is being used for its approved indication, in addition to standard of care. Furthermore, the rapid test is not being evaluated for its diagnostic accuracy (which has been determined by studies used to gain FDA approval), but rather to determine whether its use in the clinical setting can improve quality of patient care.

5.2 Randomization

Patients meeting enrollment criteria will be assigned, in a 1:1 ratio using permuted blocks, to one of the two arms outlined in Section 4.0. The randomization scheme will be stratified by site. Randomization will occur at the time the Gram stain detecting GNB is identified by the lab. Randomization will be performed by the Laboratory Technologists, using an electronic system.

5.3 Interventions

5.3.1 Notifications

Once study group is assigned, the Laboratory Technologists will immediately notify the Study Coordinator via electronic or telephone page. The Study Coordinator will then notify the Antimicrobial Stewardship (AS) team that a subject has been randomized to either arm. Each subject's medical record number, group assignment and subject ID will be recorded in an electronic log.

For subjects in both arms, the Laboratory Technologists will notify ordering clinicians by telephone when the Gram stain results are available, as is done in routine clinical practice.

Sites are responsible for notifying appropriate agencies of reportable infectious diseases per institutional policy.

5.3.2 Standard Subculture and AST

For all patients, the local standard of care for identification and AST of GNB from positive blood cultures will be performed, including standard subculture and AST as well as matrix-assisted laser desorption/ionization mass spectrometry (MALDI-TOF MS). If the primary or AS teams desire to have additional drug susceptibility information that is not routinely reported, they may request this information from the Microbiology Laboratory.

If standard culture methods detect a gram-positive organism, gram-negative cocci, and/or yeast *instead* of a gram-negative organism (as was originally detected on Gram stain), the culture result will be reported in the medical record, as per standard of care, and the subject will be considered unevaluable as he or she will not have GNB bacteremia.

5.3.3 Rapid identification and AST

For patients randomized to the rapid testing arm, testing will be performed during local laboratory business hours, using the AXDX system. Several milliliters of material from the positive bottle will be used to perform the testing, while the remainder will be used for standard of care testing. If no targets are identified using the rapid testing panel (see Table 1, Section 1.1), then identification and AST will be done through standard methods only. Combinations of bacteria/antibiotics that are reported by AXDX but not routinely reported by each laboratory will be suppressed for study patients. GNB/antibiotic combinations that are not reported by AXDX, but are routinely reported by the lab using standard of care testing, will be added to the final AST report for study patients.

If there is disagreement between the rapid AST and the standard AST results, any “intermediate” or “resistant” result will be reported, regardless of testing method. The primary team caring for the patient will be notified by phone of discrepant results, and additional susceptibility testing will be performed as needed and determined by the site Laboratory Director. Discrepant results will be reviewed by the Microbiology Laboratory Director as detailed in section 6.0. If the primary or AS teams desire to have additional drug susceptibility information that is not reported by AXDX or standard of care testing, they may request this information from the Microbiology Laboratory.

If the AXDX assay detects a gram-positive organism, gram-negative cocci, and/or yeast (that was not originally noted on Gram stain) *in addition* to GNB, the laboratory technologist will review the Gram stain. If the gram-positive organism or yeast is seen upon review, the following FDA-approved gram-positive or yeast organism identifications along with AST will be reported in the medical record: *Staphylococcus aureus*, *Staphylococcus lugdunensis*, *Enterococcus faecalis*, *Candida albicans*, *Candida glabrata*, coagulase-negative staphylococci, *Enterococcus* species, *Streptococcus* species. If the gram-positive bacteria or yeast is not seen upon review of the Gram stain, the AXDX result will not be reported, as this test is not FDA approved for clinical use if organisms are not visualized by Gram stain. If the AXDX assay detects a gram-positive organism, gram-negative cocci, and/or yeast *instead* of GNB (as was originally detected on Gram stain), the AXDX result will not be reported. In these cases, if standard culture methods detect other organisms *instead* of GNB, the standard culture result will be reported in the medical record, and the subject will be considered unevaluable as he or she will not have GNB bacteremia.

5.3.4 Antimicrobial Stewardship

All patients in both arms of the study will undergo prospective audit and feedback by the institutional AS programs. The AS physician or pharmacist will review the subject’s microbiology results and medical records. The AS provider will contact the primary service (or the consulting infectious diseases (ID) physician, if applicable) if modifications

to therapy are indicated, at any time following notification of positive Gram stain result, organism identification, and/or AST results. If the ID service is consulting on the subject, the AS team will contact the ID service rather than the primary service. If the rapid test result is ready when the AS team is unavailable (i.e. in the evening or weekend), the AS team will review the record and make recommendations at the beginning of the following working day. Local institutional treatment guidelines will be followed. Recommendations will be communicated to the treating teams via telephone or pager and documented per institutional standards. Recommendation types and acceptance rates will be recorded in the study database. Categories of recommendations include: intravenous to oral conversion, de-escalation of gram negative coverage, de-escalation of gram positive coverage, escalation of gram negative coverage, escalation of gram positive coverage, dose optimization, discontinuation of therapy, therapeutic drug monitoring, reduce/define duration of therapy, ID consultation, and other. More than one stewardship recommendation category may be chosen.

In addition to prospective audit and feedback, other routine institutional AS activities will continue, such as implementation of institutional treatment guidelines, prior authorization of restricted antibiotics, review of all patients on selected antibiotics with feedback to clinicians, and daily review of specific culture results.

5.4 Blinding

Primary service/provider: The primary service, including the prescribing provider, will be unaware of group assignment at the time of randomization, so initial antibiotic choice will not be affected by group assignment. Once rapid results become available and/or AS interventions are made, treating providers may become aware of group assignment.

The AS team and laboratory technologists will not be blinded.

5.5 Assessments

For this study, all measurements and assessments will be taken from the electronic medical record (EMR) and are done as routine standard of care practice.

5.5.1 Baseline Assessment

Once a patient is randomized, information about the patient's demographics, comorbid conditions, severity of illness (e.g. components of the Pitt Bacteremia Score¹⁸⁻²⁰), and microbiology and antimicrobial susceptibility results will be recorded. Whether a patient is on comfort care will be recorded, as determined by review of the primary physician team notes and any relevant consultations (e.g. Palliative Care).

5.5.2 Daily Evaluations

Information about additional microbiology results and antibiotic treatment will be gathered from the EMR during the three days following randomization. Suspected source and site of infection will be recorded by the AS providers.

5.5.3 Antibiotic spectrum and antibiotic intensity score

The antibiotic intensity score will be determined as follows: Each antibiotic is assigned an antibiotic spectrum rank from 1-5 (see Table 4). The antibiotic rank will be multiplied by the duration each antibiotic is received (in hours) within the first 72 hours following randomization. For patients receiving multiple antibiotics, the total antibiotic intensity

score will be the summation of the rank x duration product for each antibiotic. If a single dose of antibiotic is administered, duration will be considered 1 hour. For all antibiotics given for more than one dose, the duration will be the time of administration of the last dose minus the time of administration of the first dose (or time of randomization, if subject was receiving antibiotic at randomization) plus one hour. Patients who die before 72 hours will be assigned the highest intensity score among patients in the study who were alive at 72 hours.

Table 4. Antibiotic spectrum rank, categorized by clinical use and spectrum

Intensity score	Rank	Antibiotics
1	Narrowest	Amoxicillin, ampicillin, first-generation cephalosporins, clindamycin, dalbavancin, daptomycin, dicloxacillin, linezolid, macrolides, metronidazole, nafcillin, oritavancin, oxacillin, penicillin, quinupristin/dalfopristin, rifampin, tedizolid, vancomycin
2	Medium narrow	Amoxicillin/clavulanic acid, ampicillin/sulbactam, 2 nd -generation cephalosporins, 3 rd generation cephalosporins (except ceftazidime), PO fluoroquinolones (ciprofloxacin, moxifloxacin, levofloxacin), tetracyclines, trimethoprim-sulfamethoxazole,
3	Medium	Aminoglycosides (amikacin, gentamicin, tobramycin), ceftaroline, ceftazidime, IV fluoroquinolones (ciprofloxacin, moxifloxacin, levofloxacin), fosfomycin
4	Medium broad	Anti-Pseudomonal penicillin/penicillinase combinations, aztreonam, cefepime, ertapenem
5	Broadest	Anti-Pseudomonal carbapenems, ceftazidime/avibactam, ceftolozane/tazobactam, polymyxins, tigecycline

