7.2.3 Exploratory Analyses

- Standardized costs, obtained from the UHC/Vizient database
- The primary endpoint will be analyzed comparing patients who are:
 - in the ICU at baseline versus not in the ICU at baseline
 - neutropenic at baseline versus not neutropenic at baseline
- The primary endpoint will be analyzed excluding antibiotic modifications made within the first hour after randomization, as these changes may be in response to Gram stain result rather than AXDX result
- 30-day readmission to the index hospital
- The proportion of discrepancies (as detailed in 6.0) between rapid testing and standard of care testing among subjects who receive rapid testing (arm 2)
- Antibiotic intensity score (as detailed in 5.5.3) in the first 72 hours post randomization

- Desirability of outcome response and response adjusted for antibiotic risk within 72 hours (DOOR-RADAR) score (see Table 7 below)

Table 7. Desirability of outcome response (DOOR) ranking table.

DOOR Rank	30-day mortality	In ICU at 72h post-randomization	HO-CDI*	New resistant or hospital-acquired organism**
1	Alive	No	No	No
2	Alive	No	Yes	No
3	Alive	No	No	Yes
4	Alive	No	Yes	Yes
5	Alive	Yes	No	No
6	Alive	Yes	Yes	No
7	Alive	Yes	No	Yes
8	Alive	Yes	Yes	Yes
9	Dead	--	--	--

*HO-CDI, Hospital onset *C. difficile* infection

**Newly acquired within 30 days post-randomization, from clinically collected or surveillance cultures

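### The antibiotic intensity score counts the hours a drug was stopped as exposure whenever the same drug is restarted within 72 hours

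*Combined protocol and SAP*

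**What the plan says.** Section 5.5.3 states the quantity it wants: "The antibiotic rank will be multiplied by the duration each antibiotic is received (in hours) within the first 72 hours following randomization". With several drugs, the total "score will be the summation of the rank x duration product for each antibiotic", so there is one term per drug, not one per course.

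Duration follows two rules. The first is "If a single dose of antibiotic is administered, duration will be considered 1 hour". For drugs given more than once, "the duration will be the time of administration of the last dose minus the time of administration of the first dose", with the alternative start "or time of randomization, if subject was receiving antibiotic at randomization) plus one hour".

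Table 4 ranks drugs from 1 to 5. Rank 5 is "Anti-Pseudomonal carbapenems, ceftazidime/avibactam, ceftolozane/tazobactam, polymyxins, tigecycline"; rank 2 includes third-generation cephalosporins other than ceftazidime.

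Section 7.2.3 lists the outcome as exploratory: "Antibiotic intensity score (as detailed in 5.5.3) in the first 72 hours post randomization". Section 7.4.2 compares exploratory outcomes between arms, using the primary-outcome approach where means are of interest. None of these sections mentions gaps, separate courses or restarts.

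**The concern.** Last dose minus first dose equals time received only if the drug was given without a break. If it is stopped and the same drug is restarted before 72 h, the formula fills the break at that drug's rank. Whatever was given during the break adds its own term. The rule then departs from the quantity that the section sets out to measure.

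The error also has the wrong sign. For a rank 5 drug replaced by a rank 2 drug, each hour of narrowing should lower the score by about 5 - 2 = 3 points. If the rank 5 drug is later restarted, each such hour instead adds about 2. A participant who was narrowed for part of the window can therefore rank as more exposed than one who was never narrowed. At stake is whether this exploratory comparison of antibiotic exposure means what its label says.

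**Working it through.** The plan gives no numerical intensity score, so there is no figure to reproduce. The check applies the written rule to example regimens.

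**Inputs.** Ranks 5 and 2 come from Table 4. The duration and summation rules come from 5.5.3. Dose times are assumptions for arithmetic only; the documents give no dosing intervals.

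**Formula as written.** Score = sum over drugs of rank x (last dose - first dose + 1 h), with 1 h for a single dose.

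**Example.** Rank 5 drug at 0 and 8 h; rank 2 drug at 16 and 40 h; the same rank 5 drug again at 56, 64 and 72 h.

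- As written: (72 - 0 + 1) x 5 + (40 - 16 + 1) x 2 = 365 + 50 = 415.
- Never narrowed, rank 5 drug from 0 to 72 h: 73 x 5 = 365.
- By course, keeping the plus-one-hour convention: [(8 - 0 + 1) + (72 - 56 + 1)] x 5 + 25 x 2 = 130 + 50 = 180.
- Each drug credited until the next starts, ending at 72 h: 16 x 5 + 40 x 2 + 16 x 5 = 240.

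The overcount is 415 - 180 = 235 or 415 - 240 = 175, depending on the credit after a last dose. The 235 is the 47 h from 9 h to 56 h at rank 5. Capping the rank 5 duration at 72 h removes 5 points from both 415 and 365, so the reversal stays at 50 points.

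**Other assumed regimens.**

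| Regimen | Never narrowed | Narrowed and restarted, as written | By course |
|---|---|---|---|
| Rank 5 at 0, 8, 16 h; rank 2 at 24, 48 h; rank 5 at 64 h | 5 x 65 = 325 | 5 x 65 + 2 x 25 = 375 | 5 x 17 + 2 x 25 + 5 x 1 = 140 |
| Same times, rank 4 for the broad drug | 4 x 65 = 260 | 260 + 50 = 310 | 4 x 17 + 50 + 4 x 1 = 122 |
| Rank 5 as in the first row; rank 1 every 8 h from 24 to 56 h | 325 | 325 + 33 = 358 | 85 + 33 + 5 = 123 |

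**Generality.** In a grid of 105 stop-and-restart patterns, with both participants' last rank 5 dose at 72 h, the participant who narrowed scored higher in all 105. This follows from the rule: with the same first and last broad-drug doses, the broad-drug terms are equal and the replacement can only add.

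**Narrowing without restart.** For the first row without the 64 h dose: 5 x 17 + 2 x 25 = 135, against 325. Over a grid of switch times, the highest score after narrowing was 303, against 365 for staying on the rank 5 drug. The rule orders these participants as intended.

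**The case against.** The strongest case against is that this is a rare pattern in one exploratory outcome. The reversal needs the same drug to be restarted inside 72 h, and no restart rate is given. The primary outcome, its power and the listed secondary outcome measures are untouched. All of that stands.

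A summed by-course score is also not the truth. In the example it credits 26 + 25 = 51 of 72 h, because every course ends one hour after its last dose. This stands too, and is why the overcount is given as a range and why the fix must address the credit after the last dose.

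A reader might go further than the documents allow in three ways.

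- **Bias against rapid testing.** Only the rapid arm can have a rapid result contradicted by the standard one, in which case "The primary team caring for the patient will be notified by phone of discrepant results" (5.3.3). But both arms have MALDI-TOF identification and standard susceptibility testing (5.3.2), and stewardship may act after Gram stain, identification or susceptibility results (5.3.4). Narrowing and re-broadening can therefore occur in either arm. Section 1.2 puts standard results at 48 to 96 h after positivity, so many restarts prompted by a discrepancy would fall after the window.
- **Damage to DOOR-RADAR.** Section 7.2.3, Table 7 and 7.4.2 do not say that its antibiotic component uses this score, and the Synopsis lists another 72-hour measure, the duration of broad-spectrum gram-negative coverage.
- **Negative scores.** Applied literally, a drug last given before randomization could yield negative time. The 72-hour limit in 5.5.3 more naturally gives zero. One clarifying sentence is enough.

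**Conclusion.** The point holds for a drug stopped and restarted within 72 h. The written duration rule then counts time off the drug as exposure and adds the replacement, against the stated aim of 5.5.3. This is a stated rule that gives a wrong score and can give a wrong ordering, not merely a missing detail.

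Under the assumed dose times, the overcount is roughly 175 to 235 points per affected participant, and 415 is ranked above 365. The amount depends on the length of the gap, the ranks and the credit after a last dose. The reversal in these comparisons also assumes that the restarted drug runs as late as in the participant who never narrowed.

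The size and direction of any effect on the difference between arms cannot be derived from the documents. The consequence is confined to this exploratory outcome.

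**What to change.** In 5.5.3, compute duration for each continuous course of a drug, count only time from 0 to 72 h after randomization, and sum the courses. Prespecify:

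- the gap that ends a course;
- the time credited after each course's last dose, noting that one hour per course undercounts short courses;
- that a drug with no dose after randomization contributes no negative time.

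Apply the same program to both arms. Settle these choices before outcome data are examined, since stewardship and laboratory staff are unblinded (5.4).

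The cost is a few sentences in the plan, a modest programming change, and a gap threshold chosen in advance. All dose times in the window, not only the first and last, must be extracted from the EMR. Appendix I already schedules antibiotic administration at baseline, 24, 48 and 72 h, but does not say that every dose time is recorded, so the case report form should be checked.
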